analysis of insulin signaling. *Insulin-stimulated FFA and glucose uptake in WAT explants* from umbilical biopsies will be performed as previously established for non-human primate tissue and as shown in our previous publications and in **Figure 8**.(96-98) *Glucose uptake in skeletal muscle biopsies* will be evaluated in samples treated alone or with 10 nM insulin for 30 min and then exposed to 50 μ M 2-NBD-glucose for an additional 30 min. Samples are then washed, fixed in 4% paraformaldehyde, washed in HBSS with 50 mM CoCl₂, and stored in HBSS with 25 mM CoCl₂ until analyzed by confocal microscopy. 2-NBD-glucose incorporation into individual fibers is quantified using image J. Mean fluorescence per fiber is determined using a randomly positioned circular region of interest of cross-sectional images. *Insulin signaling pathway expression and activation* will be analyzed by preparing total protein lysates in RIPA buffer after homogenization in a motor-driven glass-glass homogenizer for muscle and in X buffer for WAT. Lysates are then subjected to standard Western immunoblotting for phosphorylated (activated) IR, Akt, and (in muscle) PKC- Θ , followed by stripping and probing with pan-IR, Akt, and PKC- Θ antibodies to determine general expression levels and for normalization of phospho-antibody signals as previously described.(24, 25, 63) We acknowledge that insulin receptor substrates (IRS)-1 and 2 are important components of the insulin signaling pathway in fat and muscle and are involved in insulin resistance, but it is our experience that analysis of IRS-1/2 activation requires significant amounts of lysate and immunoprecipitation prior to Western immunoblotting, which we are unlikely to acquire from the biopsies that will be obtained. The proposed analysis of IR, Akt, and PKC- Θ should, however, provide sufficient data to ascertain the status of the insulin-signaling pathway in samples from the different treatment groups.

V.

Statistical Analysis:

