The primary analyses to compare disease groups with healthy controls will use mixed models with a random effect for matched pair to allow for correlation between the observations on the matched observations. In addition to the random pair effect, a disease effect (disease versus healthy), and a diagnostic group effect (CPT2, VLCAD, LCHAD/TFP, MCAD), we will also incorporate a fixed effect for the order of testing (interlipid infusion tested first or second). The hypotheses focus on the comparisons between diseased individuals and their matched controls with regard to the difference in outcomes under the two conditions (glycerol vs interlipid infusion). For these analyses, we will use the difference in a given outcome (e.g., Rd uptake) between infusion conditions as the dependent variable and compare these differences between diseased and matched controls, separately for the four diagnostic groups (CPT2, VLCAD, LCHAD/TFP, MCAD). Although we will conduct a formal test of interaction of disease (disease vs healthy) and diagnostic group, we are not powered for such a test and, hence, will focus on separate inferences for the four disease groups. Note that, as indicated in the hypotheses, we expect to find differences between the controls and the CPT2, VLCAD, and LCHAD/TFP subjects, but not between the controls and the MCAD subjects. For the latter comparison, our emphasis will be on estimating the magnitude of the mean differences via 95% confidence intervals rather than formal hypothesis testing. We will use a significance level of 0.05 for each outcome comparison, with no adjustment for multiple comparisons due to the limited sample sizes. We are unable to increase sample sizes due to the small study populations and budgetary constraints, so cannot power the study to take into account the multiple comparisons. However, we will present for each outcome, both unadjusted p-values as well as p-values adjusted for the two multiple comparisons (one for each disease group) using the Holm procedure.(38)

Power Considerations:

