For each outcome, we have two measurements on every subject, one for each infusion condition. Our analyses will focus on comparisons between patients and controls of the *differences between outcomes* under the two conditions. We expect to see meaningful differences between controls CPT2, LCHAD/TFP, and VLCAD-deficient participants. These are the groups of interest for power calculations, whereas for MCAD, our aim is to provide useful descriptive information. There are two sets of correlations

between measures that need to be considered in power calculations (and statistical analyses). The first is the correlation between outcome measures on a given subject under the two infusion conditions, the second is the correlation of the differences in outcomes under the two infusion conditions, between each subject and his/her matched pair. For power calculations, we considered various values for each of these two correlations and used standard deviation estimates for each infusion condition as reported for glucose infusion rate (GIR) and for PDK4 mRNA levels (81, 94). GIR is a primary result during the HEC, closely related to insulin resistance (specific aim 1). PDK4 message is associated with our hypothesized mechanisms for insulin resistance in muscle and adipose tissue (Specific Aim 2). Mean and SD values for these outcomes in healthy controls are given in **Table 5**. We assume that normal controls and MCAD subjects will have mean outcomes as given in the table but that subjects with CPT2, VLCAD, and LCHAD/TFP disorder will have mean decreases when given the interlipid infusion that are less than 10% from that under the glycerol infusion condition for GIR and a mean increase of less than 100% for PDK4 mRNA. That is, we expect the mean change from glycerol infusion condition to be less than 5.7, and 0.18 for GIR, and PDK4 mRNA, respectively, for the CPT2, VLCAD, and LCHAD/TFP subjects.

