In **Table 6**, we show the differences between groups in mean change that can be detected with 80% power at level 0.05 when the sample size per long-chain disorders is 20. For n=10 subjects, we have adequate power for detecting expected differences for GIR and PDK4 mRNA with modest correlation between repeated observations on the same subject and between matched pairs. For GIR, even with zero correlation, we would have about 97% power at level 0.05 to detect the expected difference in change between groups (31.5 vs 5.7) with n=10. For PDK4 mRNA, we could detect the expected difference in change (-0.62 vs -0.18) with 63% power if zero correlation and with 78% power if the correlation is 0.25 between and within n=10 matched patients.

Table 5: Glucose Infusion Rate (GIR), and PDK4 mRNA/actin in healthy controls and hypothesized mean differences in subjects.				
Outcome	Glycerol Infusion	Interlipid Infusion	H_a : mean Δ In Controls and MCAD	H_a : mean Δ In VLCAD and LCHAD/TFP
GIR ($\mu\text{mol}/\text{kg}/\text{min}$) (n=9)	57.2 ± 9.3	25.7 ± 7.8	31.5	5.7
PDK4 (mRNA/actin) (n=10)	0.18 ± 0.06	0.8 ± 0.38	-0.62	-0.18

Data are mean \pm standard deviation from Roden et al and Tsintzas et al. GIR = glucose infusion rate; PDK4 = pyruvate dehydrogenase kinase 4; H_a : mean Δ = hypothesized mean difference.

Table 6: Change between glycerol infusion and interlipid infusion that can be detected between control and the VLCAD, LCHAD/TFP and CPT2 groups with 80% power at level 0.05 with n=20 subjects long-chain FAO disorders.				
Outcome	Mean Δ (Glycerol – Intralipid) Controls	Correlation between observations on the same subjects	Correlation of Δ between matched controls and patients	Mean Detectable Δ (Glycerol – Intralipid)* LCHAD/TFP subjects
GIR	31.5	.25	.25	17.6
	31.5	.50	.25	20.0
	31.5	.50	.50	22.1
PDK4 mRNA	0.62	.25	.25	0.17
	0.62	.50	.25	0.19
	0.62	.50	.50	0.27

Δ = change; * Note that changes smaller than these can be detected with greater power as smaller changes are further from the changes expected in the control groups.

Timeline: Enrollment and clamp procedures will be completed in years 1, 2, and 3. Biopsy assays and insulin signaling measures will be completed real time with collection of the muscle and adipose samples during years 1-3. In year 4, we will batch analyze stored plasma, muscle, and adipose samples for metabolomics to control for run variation of the metabolomics methods, prepare manuscripts and present the results of the project.

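### The only Aim 2 power figures are for PDK4 mRNA, which no listed assay measures and which the plan does not justify as a surrogate for the outcomes it will measure

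*Combined protocol and SAP*

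**What the plan says.** Section V, Power Considerations, says that the calculations "used standard deviation estimates for each infusion condition as reported for glucose infusion rate (GIR) and for PDK4 mRNA levels". GIR is assigned to Aim 1. PDK4 is assigned to Aim 2 with the reason that "PDK4 message is associated with our hypothesized mechanisms for insulin resistance in muscle and adipose tissue". Tables 5 and 6 both list PDK4 in the outcome column.

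For PDK4 the text says that "we could detect the expected difference in change (-0.62 vs -0.18) with 63% power if zero correlation". When both correlations are set to 0.25, the stated figure rises to 78%; each figure is for 10 matched pairs. The section describes power for GIR and PDK4 as adequate at 10 subjects, given modest correlations. No SD, effect size or power is given for any other tissue outcome.

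The measurements are set out elsewhere:

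- **Specific Aim 2 and its anticipated results:** metabolites in blood, muscle and fat; phosphorylated IR, Akt and PKC-theta; glucose and fatty acid uptake.
- **Section IV, Lab Assays:** insulin, leptin, adiponectin and FFA.
- **Section IV, Laboratory analysis of Tissue Biopsies:** explant uptake assays and protein lysates. For the lysates, "Lysates are then subjected to standard Western immunoblotting for phosphorylated (activated) IR, Akt" and PKC-theta, followed by antibodies to the total proteins.
- **Section V, Timeline:** stored plasma, muscle and fat go to metabolomics.

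**The concern.** Power belongs to a particular outcome, through its variance and its expected effect. PDK4 appears in the power section and in the title of one cited reference. It is absent from the aims, the anticipated results, the procedures table and the laboratory methods. No RNA extraction or PCR is described, and where the biopsy methods speak of expression they mean protein detected with antibodies.

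A reader of Section V would conclude that Aim 2 has a quantified power justification. In fact the plan does not say how large a difference the Western blot, uptake or metabolomics comparisons can detect. It also does not argue that their standardised effects resemble that of PDK4.

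**Working it through.** **Inputs**

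- PDK4 (Table 5): glycerol 0.18, SD 0.06; intralipid 0.80, SD 0.38.
- Hypothesised changes (Table 5): 0.62 in controls and 0.18 in long-chain patients, so the difference in change is 0.62 − 0.18 = 0.44.
- Level: the Statistical Analysis section says "We will use a significance level of 0.05 for each outcome comparison". Sidedness is not stated; two-sided is assumed.
- Pairs: 10 in the plan's PDK4 statement; 8 patients per diagnosis, each with a matched control, in Section II.

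**Step 1. Reproduce the plan's figures (paired t-test, noncentral t, n − 1 df)**

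SD of a subject's change = √(s₁² + s₂² − 2·r_w·s₁·s₂), where r_w is the within-subject correlation. SD of the pair difference = SD of change × √(2(1 − r_b)), where r_b is the correlation of changes within a pair.

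- *Zero correlation.* SD of change = √(0.0036 + 0.1444) = 0.385. SD of pair difference = 0.385 × √2 = 0.544. Standardised effect = 0.44/0.544 = 0.81. Power at n = 10 is 62.6% (stated: 63%).
- *Correlations 0.25 and 0.25.* SD of change = √(0.1480 − 2 × 0.25 × 0.06 × 0.38) = √0.1366 = 0.370. SD of pair difference = 0.370 × √1.5 = 0.453. Standardised effect = 0.44/0.453 = 0.97. Power at n = 10 is 78.1% (stated: 78%).

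The arithmetic is sound. The two stated powers amount to assuming an effect of 0.81 or 0.97 SD of the pair difference.

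**Step 2. Can these figures be moved to a measured outcome?**

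Only to an outcome with the same standardised effect. The documents give neither an SD nor an expected difference for the signalling, uptake or metabolite outcomes, so their power cannot be computed. What can be stated without an SD is the detectable difference in SD units.

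**Step 3. Detectable difference with 8 pairs**

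For 80% power at two-sided 0.05, solve for d with noncentrality d√8. The 95% CI half-width is t(0.975, df)/√8.

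| Analysis assumption | df | Detectable difference (SD of pair difference) | 95% CI half-width (SD) |
|---|---|---|---|
| Stand-alone paired t-test | 7 | 1.16 | 2.365/√8 = 0.84 |
| Separate model, one df spent on order | 6 | 1.19 | 2.447/√8 = 0.87 |
| Variance pooled over 32 pairs in four groups | 28 | 1.03 | 2.048/√8 = 0.72 |

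The Statistical Analysis section specifies mixed models with inference separately by diagnosis, but does not settle whether residual variance is pooled. The pooled row assumes equal variances across diagnoses.

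**Step 4. PDK4 itself with 8 pairs**

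With the Step 1 effects and 7 df, power is 50.5% at zero correlation and 65.7% at 0.25 and 0.25.

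**The case against.** The strongest reply is that PDK4 was chosen as a stand-in. It is a tissue readout with published SDs under both infusions, whereas the explant uptake data shown in the protocol come from rhesus macaques. A stand-in is not meaningless, since its power transfers to any outcome with a similar standardised effect. That stands, so a reader who inferred that the PDK4 figures tell us nothing about any Aim 2 outcome would go too far. But the plan neither calls PDK4 a surrogate nor defends the transfer. A link to the hypothesised mechanism is a statement about biology; it does not show that mRNA/actin variability resembles that of blots, fluorescence or metabolite peaks.

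A PDK4 assay might also be run on stored tissue, because one adipose aliquot is kept for unspecified later analysis. If that is intended, it needs to be written down; the Timeline names only metabolomics for stored samples.

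A reader might further infer that a null tissue result will be reported as evidence of no effect. The documents do not say so. For MCAD, where no difference from controls is expected, they put the emphasis on 95% confidence intervals. For the long-chain groups a difference from controls is predicted, so a null would fail to support the hypothesis.

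Finally, the 1.16 SD figure is a consequence of 8 pairs and would be the same if PDK4 were assayed. It does not measure the harm of choosing PDK4. It is what the plan could truthfully report in place of the PDK4 figures.

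**Conclusion.** The point holds as a gap in the Aim 2 power justification. The stated 63% and 78% are correctly calculated, but for an outcome with no listed assay. They would apply to a measured outcome only if its difference in change were about 0.81 to 0.97 SD of the pair difference, and the plan never asserts that. With the planned 8 pairs per diagnosis, 80% power needs about 1.16 SD (1.03 to 1.19 SD across the analysis assumptions above), which is larger than the effect implicit in either stated figure.

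This rests on two-sided testing, roughly normal pair differences, complete pairs, and the absence of an mRNA assay from the text available.

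Two limits apply. Aim 1 is unaffected, because GIR comes directly from the clamp. The inconsistency between 8, 10 and 20 subjects in the enrolment and power text is a separate issue and is not counted here.

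**What to change.** Stop presenting the PDK4 figures as power for Aim 2. In their place, state for the measured tissue outcomes that 8 pairs per diagnosis give 80% power for a difference in change of about 1.16 SD of the pair difference, with a 95% CI half-width of about 0.84 SD. Name the analysis assumed, or give the ranges 1.03 to 1.19 SD and 0.72 to 0.87 SD.

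If PDK4 is meant to be an outcome, add its assay to the laboratory methods, name it among the Aim 2 outcomes, and restate its power at 8 pairs: about 50% at zero correlation and 66% at 0.25 and 0.25. If it is meant only as a surrogate, say so and justify the assumed standardised effect for the outcomes it represents.

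Recasting Aim 2 as estimation is optional; this gap does not require it. Removing or relabelling the figures costs only protocol and SAP wording and needs no more participants, though the Aim 2 statement becomes less favourable. Adding a PDK4 assay would also use tissue and laboratory work, and the methods already describe biopsy lysate as limited.

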Inclusion Criteria: 32 subjects with a confirmed diagnosis of VLCAD (n=8), CPT2 (n=8) LCHAD/TFP (n=8), or MCAD (n=8) deficiency will be recruited for this study. Subjects must be \geq 18 years of age, and be willing to complete 2 CRC admissions for hyperinsulinemic euglycemic clamp studies and muscle and adipose tissue biopsies. Subjects with disorders in FAO will be recruited to participate in this study through announcements on the FAO family support network website, through OHSU's clinical population, and through letters sent to metabolic specialists across the US. Inclusion and exclusion criteria are in **Table 2**.

Confirming the Diagnosis: Each subject must have a confirmed diagnosis of carnitine palmitoyltransferase 2 (CPT2), very long-chain acylCoA dehydrogenase (VLCAD), long-chain 3-hydroxyacyl CoA dehydrogenase (LCHAD), trifunctional protein (TFP), or medium-chain acyl-CoA dehydrogenase (MCAD) deficiency. Diagnosis of a disorder in fatty acid oxidation will be confirmed by obtaining medical record results of acylcarnitine profiles, fatty acid oxidation probe studies in cultured fibroblasts and/or mutation analysis (44, 71). Establishing the diagnosis of these disorders is a complex process that varies across metabolic centers in the US. Not all potential subjects will have had a skin biopsy and FAO probe studies in cultured fibroblasts. In many cases mutation analysis can identify only one recognized mutation in the sequenced exons of the gene. Thus, a combination of methods is most often used to establish the diagnosis. If two of the three diagnostic tests suggest a diagnosis of CPT2, VLCAD, LCHAD/TFP, or MCAD, the subject will be eligible to participate in the trial (Table 3).

Table 2: Participant Selection Criteria				Exclusion Criteria: Subjects with CPT2, VLCAD, LCHAD/TFP, or MCAD deficiency may not be actively participating in another research project that prohibits their participation in this study such as a project that requires a specific diet or supplement that must be consumed daily. All subjects will be screened for anemia prior to study participation. Female subjects of childbearing potential will be screened for
Subjects with an FAO disorder		Matched controls		
Inclusion criteria	Exclusion criteria	Inclusion criteria	Exclusion criteria	

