Confirmed CPT2, VLCAD, LCHAD, TFP or MCAD	Hgb <10g/dl INR>1.20 PTT>36 seconds Platelets<150 K/mm ³	Same gender and similar age/BMI as subject with FAO disorder	Hgb <10g/dl INR>1.20 PTT>36 seconds Platelets<150 K/mm ³	
≥18 years	Pregnant /lactating females	≥18 years	Endocrine disorder such as diabetes, or untreated thyroid disease	
Ability to travel to OHSU	Endocrine disorder such as diabetes, or untreated thyroid disease	Good health, exercise < 30 min, 3 x per week for 2 weeks prior to study visits.	Cardiovascular disease or elevated plasma lipids	
Ability and willingness to complete protocol	Cardiovascular disease or elevated plasma lipids	Ability and willingness to complete protocol	Taking lipid lowering meds	
	Regularly taking meds that strongly affect bleeding, bruising or platelets.		Regularly taking meds that strongly affect bleeding, bruising or platelets	

pregnancy. Anemic (Hgb < 10 g/dl) or pregnant subjects will be excluded from the study. Subjects regularly taking medications that strongly affect bleeding, bruising, or platelets such as Coumadin, Plavix, Aggrenox, Ticlid, Agrylin, Xagrid, Aricept, Namenda, Exelon, Razadyne, or aspirin will be excluded from the study. Subjects may not have diabetes or be on medications to treat diabetes. We do not anticipate any subjects with CPT2, VLCAD, or LCHAD/TFP will have diabetes, as it has never been reported. Several cases of diabetes have been mentioned on disease specific list serves among subjects with MCAD deficiency.

Table 3: Medical Records to Confirm the Diagnosis				Matched Control Subjects: Inclusion criteria: In addition, 32 age-, sex-, and BMI-matched
Disorder	Acylcarnitine Profiles	Fatty acid oxidation Probe studies	Mutation analysis	
VLCAD/CPT2	↑ C14:0 or C14:1	↓ FAO flux with ↑ disease specific acylcarnitines	1 or 2 known mutations in specific gene	
LCHAD/TFP	↑ OH-acylcarnitines			
MCAD	↑ C8:0 or C10:0			

controls will be recruited to participate in the study through local newspaper and OHSU web site announcements. Control subjects must be a similar age, sex and BMI (± 2 kg/m²) as a study subject with a FAO disorder, be able to complete and comply with the protocol, and be in good health. Subjects must be weight stable (± 5 lbs) for the past 3 months and exercise < 30 minutes, three times a week (low activity) for two weeks prior to each study visit.

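### Power is stated for 10 matched pairs (Table 6 labelled n=20), but 8 pairs per diagnosis are enrolled and tested separately; PDK4 power is then about 50%/66% or 60%/76%, not 63%/78%

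*Combined protocol and SAP*

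**What the plan says.** Section II, Study Population, fixes enrolment: "32 subjects with a confirmed diagnosis of VLCAD (n=8), CPT2 (n=8) LCHAD/TFP (n=8), or MCAD (n=8) deficiency will be recruited for this study". The paragraph on matched controls adds "In addition, 32 age-, sex-, and BMI-matched" controls, which makes 8 matched pairs per diagnosis.

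Section V, Statistical Analysis, plans an interaction test of disease by diagnostic group but says "we are not powered for such a test and, hence, will focus on separate inferences for the four disease groups". It also explains that group size is fixed by feasibility: "We are unable to increase sample sizes due to the small study populations and budgetary constraints".

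The Power Considerations text then uses two other sample sizes. It introduces Table 6 as the case "when the sample size per long-chain disorders is 20. For n=10 subjects, we have adequate power for detecting expected differences", and the table title repeats "with 80% power at level 0.05 with n=20 subjects long-chain FAO disorders". For GIR it says "we would have about 97% power at level 0.05 to detect the expected difference in change between groups (31.5 vs 5.7) with n=10". Turning to the second outcome, PDK4 mRNA, it says the expected difference could be detected "with 63% power if zero correlation and with 78% power if the correlation is 0.25 between and within n=10 matched patients".

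**The concern.** Neither 10 nor 20 is the number enrolled per diagnosis (8), nor the long-chain total (24). A reader cannot find the power of the design that will be run. The printed figures belong to a design with more pairs than are enrolled, so they are too favourable if they were calculated as labelled in the text.

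This matters most for Aim 2. PDK4 mRNA is its only power basis, its printed power already sits below 80% at the two settings quoted, and the text nevertheless calls power adequate at modest correlation. Section III and the laboratory methods in Section IV describe immunoblots for IR, Akt and PKC-theta, glucose and FFA uptake assays, and metabolomics, but no PDK4 or mRNA assay. For Aim 1, power is given only for GIR, and not for Rd, Ra or the spectroscopy measures of lipid.

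**Working it through.** **Inputs (Table 5 and the power text).** PDK4 SDs are 0.06 (glycerol) and 0.38 (intralipid), with a difference in change of 0.62 − 0.18 = 0.44. GIR SDs are 9.3 and 7.8, with a difference in change of 31.5 − 5.7 = 25.8. Level 0.05, taken as two-sided because that reproduces the printed PDK4 values. Correlations are written within-subject/between-pair.

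**Formulas.**
- Var(change) = s1² + s2² − 2·rw·s1·s2
- SD of the patient-minus-control difference in change = √[2·Var(change)·(1 − rb)]
- Noncentrality = effect ÷ (SD/√n); power from the noncentral t distribution

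**Step 1: reproduce the PDK4 figures at 10 pairs (9 df).**
- 0/0: Var = 0.0036 + 0.1444 = 0.1480; pair SD = √(2 × 0.1480) = 0.544; noncentrality = 0.44/(0.544/√10) = 2.56; power 62.6% (printed 63%).
- .25/.25: Var = 0.1480 − 0.0114 = 0.1366; pair SD = √(2 × 0.1366 × 0.75) = 0.453; noncentrality 3.07; power 78.1% (printed 78%).

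The PDK4 rows of Table 6 come out at 0.169/0.188/0.268 with 10 pairs (printed 0.17/0.19/0.27). With 20 pairs they would be 0.321/0.334/0.386. The PDK4 rows are therefore 10-pair values. The 20 may count both members of 10 pairs, although the text says 20 per disorder. The firm conflict is 10 pairs against 8.

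**Step 2: PDK4 power at 8 pairs.** Noncentrality falls to 2.29 at 0/0 and 2.75 at .25/.25. The analysis section leaves open whether each diagnosis is tested alone (7 df) or as a contrast from one model pooling residual variance over 32 pairs (32 − 4 = 28 df), so both are shown.

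| Correlations | 10 pairs, paired | 8 pairs, paired | 10 pairs, pooled (36 df) | 8 pairs, pooled (28 df) |
|---|---|---|---|---|
| 0/0 | 62.6% | 50.5% | 70.2% | 59.8% |
| .25/.25 | 78.1% | 65.7% | 84.9% | 75.6% |
| .50/.25 | 81.5% | 69.4% | 87.8% | 79.2% |
| .50/.50 | 93.7% | 85.3% | 96.9% | 92.4% |

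Like for like at the first two settings, 8 pairs instead of 10 costs about 12 points (paired) or 9 to 10 points (pooled). A simulation of 200,000 runs agreed with the 8-pair columns to within 0.2 points. Pairs needed for 80%, in table order: 15, 11, 10, 8 (paired) or 13, 9, 9, 6 (pooled). With both correlations equal, 80% needs about 0.28 at 10 pairs (paired), but 0.44 (paired) or 0.31 (pooled) at 8 pairs.

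**Step 3: GIR.** With the Table 5 SDs, 10 pairs give 98.8% and Table 6 rows of 18.6/21.0/22.9, against the printed 97% and 17.6/20.0/22.1. A glycerol SD near 10.5 with 10 pairs would reproduce all four printed figures (97.4%; 17.6/20.0/22.1). That SD is only an inference: other SD pairs fit at 8 or 9 pairs, so the rows fix neither n nor SD. At 8 pairs and zero correlation, GIR power is 95.2% (7 df) or 98.4% (28 df) with the Table 5 SDs, and 92.0% or 96.8% with a glycerol SD of 10.5.

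**The case against.** The best counter-argument is that the planned mixed model has group and interaction terms, which cannot be fitted within one diagnosis, so it most naturally pools variance. On that reading 8 pairs give 60%/76%, only 2 to 3 points below the printed 63%/78%. The gap to the printed numbers is indeed that small if the model is pooled. But it sets a pooled 8-pair figure against a paired 10-pair one. On the pooled basis throughout, the loss is 70%/85% to 60%/76%. The pooled figures may also be slightly generous: if patient and control orders are randomised independently within pairs, which the plan does not settle, a simulation with the order term gave 58.8%/73.4%.

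Second, 0.44 is a bound. The plan expects a PDK4 change below 0.18 in long-chain patients, and smaller changes have more power. With a change of 0.10, 8 pairs at .25/.25 give about 80% (paired) or 88% (pooled). This stands, but the plan quotes its own 63% and 78% at the bound, so the comparison here is fair.

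Third, the failure to reach 80% is narrow at one setting (79.2% pooled at .50/.25), the term modest is undefined, and the plan prints its sub-80% figures openly. These points soften the criticism without removing it.

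Finally, sample size is fixed by feasibility and GIR is well powered. Both are true. The point concerns the accuracy of the power statement, not the enrolment target.

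**Conclusion.** The concern holds. Power is stated for 10 pairs and Table 6 is labelled n=20, while 8 pairs per diagnosis are enrolled and tested separately. At 8 pairs PDK4 power at 0/0 and .25/.25 is about 50%/66% (paired) or 60%/76% (pooled), and the claim of adequate power at modest correlation is unsupported. The GIR claim holds in substance, above 90% at zero correlation on every basis tried, but it covers GIR only.

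These figures assume the Table 5 SDs (with the GIR alternative shown), a two-sided 0.05 level without multiplicity adjustment, equal variances across groups for the pooled version, and no lost pairs. With 7 complete pairs the paired PDK4 figures would be 43.6% and 57.7%. This should be fixed, but it does not threaten the conduct of the study.

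**What to change.** 1. Replace the n=10 and n=20 labels and restate the power text and Table 6 for 8 matched pairs in each long-chain diagnosis. MCAD stays descriptive.
2. Before printing new numbers, reconcile the GIR SD between Table 5 and the calculation, and state whether the per-diagnosis test is a paired analysis or a contrast from one pooled model. If pooled, also state whether pair members share an infusion order. Then print the matching set (Table 6 rows in the order .25/.25, .50/.25, .50/.50):

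| Outcome | Paired, 7 df | Pooled, 28 df |
|---|---|---|
| PDK4 power (0/0, .25/.25) | 50%, 66% | 60%, 76% |
| PDK4 Table 6 rows | 0.10/0.12/0.21 | 0.16/0.18/0.26 |
| GIR power (0/0), Table 5 SDs | 95% | 98% |
| GIR Table 6 rows, Table 5 SDs | 16.6/19.3/21.5 | 18.3/20.6/22.6 |
| GIR power (0/0), if glycerol SD was about 10.5 | 92% | 97% |
| GIR Table 6 rows, if glycerol SD was about 10.5 | 15.3/18.1/20.6 | 17.2/19.6/21.8 |

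The pooled column does not include any loss of precision from the order term.

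3. Withdraw the adequacy claim for PDK4 at modest correlation.
4. Label PDK4 as a literature proxy with no described assay, or base Aim 2 power on an outcome that has one.

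The cost is protocol wording, one recalculated table and a check of the GIR SD. No extra patients are needed and the analysis does not change. The stated PDK4 power becomes less favourable.
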